9.3.2 Analysis of Secondary Efficacy Variables

9.3.2.1 Definition of Secondary Efficacy Variables

Proportion of subjects with $\geq 30\%$, $\geq 50\%$ reduction in the weekly average of daily pain intensity on the 11-point NRS, as reported in the daily diary, at Week 6: The percentage reduction in the weekly average of daily pain intensity will be calculated as following:

$100 \times (\text{daily pain intensity score at baseline} - \text{the weekly average of daily pain intensity score at Week 6}) / \text{daily pain intensity score at baseline}$.

Change from baseline in the DSIS at Week 6: The change from baseline in the DSIS at Week 6 is the change from baseline in the weekly average of daily sleep interference score on the DSIS, as reported in the daily diary at Week 6. The weekly average of DSIS will be calculated by averaging the nonmissing daily sleep interference scores in each week. If the count of nonmissing daily sleep interference scores is less than 4 in a week, the weekly average of daily sleep interference on the DSIS will be set to missing.

Proportion of subjects categorized as improved at Week 6 on the PGIC assessment: The assessment consists of a single item on a 7-point scale from 1 (very much improved) to 7 (very much worse). Subjects will be categorized as following:

- 1 - 2 reported on the PGIC assessment will be categorized as “improved”;
- 3 - 4 reported on the PGIC assessment will be categorized as “no change”;
- 5 - 7 reported on the PGIC assessment will be categorized as “worse”.

Change from baseline in pain intensity on the 11-point NRS, as reported at study visits, at Week 6: Change from baseline in pain intensity will be calculated at each post-baseline visit (Day 7, Week 3 and Week 6) following the general definition of the baseline and change from baseline in Section 9.1.

9.3.2.2 Secondary Analyses

Proportion of subjects with $\geq 30\%$ reduction in the weekly average of daily pain intensity on the 11-point NRS, as reported in the daily diary, at Week 6: This variable will be evaluated using descriptive statistics by treatment group.

[figure not shown]
Proportion of subjects with $\geq 50\%$ reduction in the weekly average of daily pain intensity on the 11-point NRS, as reported in the daily diary, at Week 6: Analysis of this variable will be the same as described for proportion of subjects with $\geq 30\%$ reduction.

[figure not shown]
In addition, the proportion of subjects with $\geq 70\%$ reduction in the weekly average of daily pain intensity at Week 6 will also be analyzed in the same way as described for the proportion of subjects with $\geq 30\%$ reduction.

Change from baseline in the DSIS at Week 6: Analysis of this variable will be based on an MMRM similar to the analysis of the primary efficacy variable. Weekly average of daily DSIS score at each week will be included in the model as the dependent variable.

Proportion of subjects categorized as improved at Week 6 on the PGIC assessment: This variable will be evaluated using descriptive statistics by treatment group.

Change from baseline in pain intensity on the 11-point NRS, as reported at study visits, at Week 6: Analysis of this variable will be based on an MMRM similar to the analysis of the primary efficacy variable. The change from baseline in NRS at each post-baseline visit (Day 7, Week 3 and Week 6) will be included in the model as the dependent variable.

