6.1.2 Secondary Efficacy Endpoints

- Proportion of subjects with $\geq 30\%$ reduction in the weekly average of daily pain intensity on the 11-point NRS, as reported in the daily diary, at Week 6
- Proportion of subjects with $\geq 50\%$ reduction in the weekly average of daily pain intensity on the 11-point NRS, as reported in the daily diary, at Week 6
- Change from baseline in the Daily Sleep Interference Scale (DSIS) at Week 6
- Proportion of subjects categorized as improved at Week 6 on the patient global impression of change (PGIC) assessment
- Change from baseline in pain intensity on the 11-point NRS, as reported at study visits, at Week 6

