9 STATISTICAL ANALYSIS

9.1 General Considerations

The Schedule of Assessments is provided in Section 3 of CSP. The precision standards for reporting safety and efficacy variables are provided in an internal Biometrics document that specifies the programming rules including the precision for derived variables.

All individual subject data, including those derived, for subjects who were randomized or received at least 1 dose of study drug, i.e. All Subjects Set, will be presented in individual subject data listings as described.

Continuous variables will be summarized using the following descriptive summary statistics: the number of subjects (n), mean, standard deviation (SD), standard error (SE), median, minimum value (min), and maximum value (max).

Categorical variables will be summarized using counts and percentages.

Baseline value for the NRS via daily diary and the DSIS will be defined as the average score of at least 4 nonmissing scores from Day -7 to Day -1. For all other variables baseline will be defined as the most recent nonmissing measurement collected before the initial administration of study drug unless specified otherwise.

Change (absolute change) from baseline will be calculated as post-baseline value – baseline value unless otherwise specified.

Treatment-emergent (TE) Period will be defined as the time from dosing with study drug until the following time point:

- For enrolled subjects who have a Safety Follow-up Visit: through the Safety Follow-up Visit
- For enrolled subjects who do not have a Safety Follow-up Visit, the earliest of
 - 35 days after the last dose of study drug, or
 - the ETT Visit if that visit is 3 weeks or later following the last dose of study drug (see Section 9.1.5 of CSP)

Unscheduled visits: Unscheduled visit measurements will be included in analysis as follows:

- In scheduled visit windows per specified visit windowing rules.
- In the derivation of baseline/last on-treatment measurements.
- In the derivation of maximum/minimum on-treatment values and maximum/minimum change from baseline values for safety analyses.
- In individual subject data listings as appropriate.

Visit windowing rules: The analysis visit windows for protocol-defined visits are provided in [Appendix A](#).

Incomplete/missing data will not be imputed, unless otherwise specified.

Outliers: No formal statistical analyses will be performed to detect or remedy the presence of statistical outliers, unless specified otherwise.

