9.2.2 Demographics and Baseline Characteristics

Demographics, medical history and baseline characteristics will be summarized overall and by treatment group based on the FAS.

Demographic data will include the following:

- Age (in years)
- Sex (male, female)
- Ethnicity (Hispanic or Latino, not Hispanic or Latino, and not collected per local regulations)
- Race (White, Black or African American, Asian, American Indian or Alaska Native, Native Hawaiian or Other Pacific Islander, not collected per local regulations, Other and Multiracial (if more than 2 races reported from a subject))

Baseline characteristics will include the following:

- Weight (kg)
- Height (cm)
- BMI (kg/m²)

- Diagnosis of diabetes (Yes, No)

Disease characteristics will include the following:

- Pain intensity at baseline as recorded on the NRS
- Daily sleep interference at baseline as recorded on the DSIS

Small fiber neuropathy history will include the following:

- Distribution of the symptoms (stocking/glove distribution, non-length dependent)
- The small fiber neuropathy symptoms have been present for ≥ 3 months (Yes, No)
- Quality of the small fiber neuropathy symptoms (burning, sharp stabbing, throbbing, cold sensation, itch, loss of sensation and other)
- Autonomic features associated with the small fiber neuropathy (Yes, No)

Medical history will be summarized by MedDRA system organ class (SOC) and preferred term (PT).

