9.3.1.2 Primary Analysis

The primary analysis of the primary endpoint will be a within-group treatment comparison in the VX-150 treatment group. The analysis will be conducted using a mixed-effects model for repeated measures (MMRM). The between-group treatment comparison will also be generated using the same MMRM.

The model will include the change from study baseline at each week in the weekly average of daily pain intensity score as the dependent variable; treatment, sex, diagnosis of diabetes, week, and treatment-by-week interaction as fixed effects and baseline pain intensity score as a covariate. The model will be estimated using restricted maximum likelihood. The denominator degrees of freedom for the F-test for fixed effects will be estimated using the Kenward-Roger approximation. In the model, an unstructured covariance matrix will be assumed to model the within-subject variability. If there is a convergence problem due to use of an unstructured covariance matrix, the unstructured covariance matrix will be replaced by a compound symmetric covariance matrix to model the within-subject variability.

Conditional on the observed data and covariates, missing data will be assumed to be missing at random; consequently, no imputation of missing data will be performed.

The post-baseline raw values and the change from baseline at each week will be summarized descriptively (n, mean, SD, SE, median, minimum, and maximum).

The adjusted mean (SE), corresponding 95% 2-sided confidence interval (CI) and 2-sided *P* value for VX-150 treatment group in change from study baseline in weekly average of daily NRS at Week 6 will be provided. The CI will first be used to facilitate the comparison with 0; this will be followed by a comparison with 0.8. Furthermore, the adjusted mean (SE) and corresponding 95% CI for the treatment difference between VX-150 and placebo at Week 6 will be provided.

In addition, adjusted means (SE) and 95% CIs for all within-group treatment and between-group treatment comparisons at other weeks will also be provided.

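### SAP 9.3.2.2 names the weekly DSIS score, not its change from baseline, as the model outcome for the DSIS endpoint: probably a drafting slip, minor, and cured by one sentence

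*SAP*

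**What the plan says.** The endpoint is stated the same way throughout. SAP 6.1.2 lists "Change from baseline in the Daily Sleep Interference Scale (DSIS) at Week 6", and Protocol 7.2 and 12.3.3.2 agree. SAP 9.3.2.1 defines the variable: "The change from baseline in the DSIS at Week 6 is the change from baseline in the weekly average of daily sleep interference score". SAP 9.1 supplies the baseline ("Baseline value for the NRS via daily diary and the DSIS will be defined as the average score of at least 4 nonmissing scores", over Day -7 to Day -1) and the direction of subtraction ("Change (absolute change) from baseline will be calculated as post-baseline value", minus the baseline value).

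The DSIS paragraph in SAP 9.3.2.2 carries the change-from-baseline label and says the model is similar to the primary one. Its next sentence then gives the outcome as: "Weekly average of daily DSIS score at each week will be included in the model as the dependent variable".

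The SAP's other two repeated-measures models name the change. For the primary model, SAP 9.3.1.2 says: "The model will include the change from study baseline at each week in the weekly average of daily pain intensity score as the dependent variable". For pain reported at study visits, SAP 9.3.2.2 says: "The change from baseline in NRS at each post-baseline visit (Day 7, Week 3 and Week 6) will be included in the model".

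The only baseline covariate named in SAP 9.3.1.2 is baseline pain intensity. The DSIS paragraph names none, although baseline DSIS is defined in SAP 9.1 and listed for summary in SAP 9.2.2 ("Daily sleep interference at baseline as recorded on the DSIS").

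**The concern.** The sentence that spells out the dependent variable gives a different variable from the endpoint. A programmer who follows it would fit the weekly score and report an adjusted Week 6 mean that is not the stated endpoint.

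This matters most for the within-group result, because the primary analysis that the DSIS model is meant to resemble is a within-group one, with the confidence interval compared first with 0. DSIS runs from 0 (none) to 10 (severe) according to Protocol 9.3.3, and change is post-baseline minus baseline, so improvement is a negative change. A weekly average score can never be negative. An interval for the score that lies above 0 would say nothing about improvement.

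The unnamed baseline covariate is a second, smaller ambiguity. It determines whether the between-group result also depends on which outcome is fitted.

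**Working it through.** The documents state no figure for the DSIS analysis, so there is nothing to reproduce. The check is algebra, followed by a numerical confirmation on assumed data.

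**Range.** The score lies in [0, 10]. Change is score minus baseline, each in [0, 10], so it lies in [-10, 10], with improvement below 0.

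**Baseline DSIS in the model.** For subject i in week t, let Y be the weekly score, B the baseline DSIS and x the remaining terms (treatment, sex, diabetes, week, treatment by week):

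- Score model: Y_it = x_it'β + γB_i + e_it
- Change model: Y_it - B_i = x_it'β + (γ - 1)B_i + e_it

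The two models have the same design and the same residuals. They therefore give the same covariance estimate, treatment terms and standard errors. Only the baseline slope changes, from γ to γ - 1. Adjusted means evaluated at the mean baseline differ by γ × mean(B) - (γ - 1) × mean(B) = mean(B). Missing weeks do not alter this, because the same B_i is subtracted from every observed week.

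**Baseline pain as the only baseline covariate.** Subtracting B_i is no longer absorbed by a term in the model. The two between-group estimates then differ by roughly the between-arm difference in baseline DSIS after adjustment for pain, sex and diabetes. This is approximate, because the covariate slopes are common to all weeks and weighted by the estimated covariance. Under randomisation the expected difference is zero.

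**Numerical confirmation.** All values are assumed: one simulated data set, 45 per arm, 6 weeks, dropout leaving 34 and 38 at Week 6, REML with unstructured covariance, mean baseline DSIS 5.880. Entries are Week 6 estimates (SE).

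| Baseline covariate | Outcome | VX-150 adjusted mean | Between-group |
|---|---|---|---|
| DSIS | change | -1.286 (0.293) | -0.266 (0.422) |
| DSIS | score | 4.595 (0.293) | -0.266 (0.422) |
| Pain only | change | -1.292 (0.303) | -0.278 (0.437) |
| Pain only | score | 4.683 (0.298) | -0.096 (0.429) |

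With baseline DSIS, the within-group gap before rounding is 4.5945 + 1.2857 = 5.880, the mean baseline, and the between-group result is identical. With baseline pain only, the between-group gap is -0.096 + 0.278 = 0.182. In the same data without dropout it is -0.0878 + 0.2142 = 0.126, against a covariate-adjusted baseline imbalance of 0.125.

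A second assumed data set (mean baseline 4.957) shows the same identity with baseline DSIS in the model: 3.939 for score and -1.018 for change, a gap of 4.957, with a between-group estimate of 0.236 (SE 0.266) under both.

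These figures confirm the identities. They do not predict the size of any effect in this trial.

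**The case against.** The strongest reply is that the documents already settle the matter. The paragraph label names the change, the text says the model is for that variable, the variable is defined as a change one section earlier, and the primary model it points to uses change. All of this stands. It makes a slip the likely explanation, and it means the sentence at issue is not the only indication of the outcome. It does not remove the problem, because the explicit sentence is the more specific instruction and says something else.

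It is also fair that DSIS is one of several secondary endpoints in a proof-of-concept study, that no stated success rule depends on it, and that a table of supposed changes with all means positive would probably be noticed. If the primary analysis's descriptive summaries carry over too, change would still be reported descriptively. This supports a minor rating.

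A reader might infer more than the documents support:

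- **That a DSIS test against 0 is planned and invalid.** SAP 9.3.2.2 states no such comparison for DSIS. It arises only if similarity to the primary analysis imports it.
- **That the treatment comparison is biased.** It is not. With baseline DSIS in the model the two outcomes give the same estimate; without it, they differ by chance imbalance.
- **That adjusting for baseline pain alone would be invalid.** A change model with that covariate is still valid. Naming baseline DSIS is a clarification that makes the between-group result independent of the wording.

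**Conclusion.** The sentence is wrong as written, and the consequence is minor. It contradicts the endpoint definition in both documents and is probably a drafting slip. Taken literally, the model-based within-group result at Week 6 would be a level rather than a change, too high by exactly the mean baseline DSIS when baseline DSIS is the covariate. Its size cannot be given from the documents.

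The between-group estimate is unaffected if baseline DSIS is a covariate. If baseline pain is the only one, it shifts by approximately the covariate-adjusted chance imbalance, which is not bias. The exact identities assume a single main-effect baseline term, the same subjects in both fits, and adjusted means evaluated at the same mean baseline. The primary endpoint, sample size and power table are untouched.

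**What to change.** Replace the sentence in SAP 9.3.2.2 with wording to this effect:

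> The dependent variable is the change from baseline in the weekly average DSIS score at each week. Baseline DSIS (Day -7 to Day -1 average) replaces baseline pain intensity as the baseline covariate; all other terms are as in the primary model.

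The covariate set should be fixed and not left optional. In the second assumed data set, adding baseline pain to baseline DSIS moved the between-group estimate from 0.236 (SE 0.266) to 0.304 (SE 0.259), whereas the choice between score and change moved it not at all.

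The cost is this one change of wording. Baseline DSIS is already collected and defined, so nothing changes operationally. SAP section 4 has the plan finalised before database lock; if lock has passed, the same section requires the change to be documented in the clinical study report.

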9.4 Safety Analysis

The overall safety profile of VX-150 will be assessed in terms of the following safety and tolerability endpoints:

- Incidence of treatment-emergent adverse events (TEAEs)
- Clinical laboratory values
- ECG outcomes

- Vital signs
- C-SSRS

Safety analyses will be based on the Safety Set.

All safety data will be presented in individual subject data listings.

Safety analyses will be based on the Safety Set and subjects will be analyzed according to the treatment they actually received. In an unexpected scenario that a subject may receive more than one treatment in the study, the following algorithm will be used to define subject's actual treatment: for any dosed subjects, the actual treatment is defined as VX-150 if the subject received any VX-150 treatment, regardless of the randomized treatment assignment. Otherwise, the actual treatment is defined as placebo only if the subject receives placebo at all visits in the study.

9.4.1 Adverse Events

AEs will be coded according to MedDRA. The number and percentage of subjects experiencing an AE will be summarized by the MedDRA System Organ Class and preferred term, as well as by treatment group. AEs will be classified as pretreatment or treatment-emergent as follows:

Pretreatment AEs are defined as AEs that were reported or worsened after signing the ICF up to the start of study drug dosing.

Treatment-emergent AEs are defined as AEs that were reported or worsened on or after the first dose date of study drug through the end of the TE period.

Details for imputing missing or partial start dates of adverse events are described in [Appendix C](#).

Only TEAEs will be summarized in tables. All summaries of TEAEs will be presented by the severity of the AE and relationship to the study drug. Some rules that will apply to the summarization of AEs are (1) a subject with multiple occurrences of the same AE or a continuing AE will only be counted once; (2) only the maximum severity level will be presented in the severity summary; and (3) only the strongest relationship level will be presented in the relationship summary. An AE with relationship missing is counted as related AE.

SAEs, AEs leading to death, and AEs leading to study drug interruption, study drug discontinuation, and study discontinuation will be listed separately. All AEs through Safety Follow-up will be listed in an individual subject data listing, including pretreatment AEs.

9.4.2 Clinical Laboratory Assessments

All statistical analyses of laboratory values will be performed using International System of Units. The raw values and change from baseline values for the continuous hematology, clinical chemistry will be summarized by treatment group at each scheduled visit. The threshold value criteria for hematology and clinical chemistry laboratory tests are provided in [Appendix D](#). The number and percentage of subjects with at least 1 hematology and clinical chemistry laboratory measurement meeting the threshold value criteria will be summarized

by treatment group at each scheduled visit. Coagulation results will be summarized by treatment group at each scheduled visit. The number and percentage of subjects with abnormal coagulation values at each scheduled time point will be summarized.

A listing containing individual subject hematology and clinical chemistry laboratory measurements meeting the threshold value criteria at any visit will be provided. For each subject in the listing, laboratory measurements at all visits will be included. This listing will include data from scheduled and unscheduled time points. Abnormal coagulation and urinalysis results also will be listed separately. For each subject in the listing, coagulation and urinalysis results at all visits will be included. Results of the urine/serum pregnancy test will be presented in individual subject data listings only.

Clinically significant abnormal laboratory findings will be reported as AEs.

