12.3.4.2 Clinical Laboratory Assessments

All statistical analyses of laboratory values will be performed using SI units. Hematology (including coagulation) and clinical chemistry results will be summarized by treatment group at each scheduled time point. The number and percentage of subjects with at least 1 potentially clinically significant (PCS) event will be summarized by treatment group at each scheduled time point. A listing containing individual subject laboratory measurements meeting the PCS criteria will be provided. For each subject in the listing, laboratory measurements at all time points will be included. The PCS criteria for clinical laboratory data will be provided in the SAP. Urinalysis results will be listed only in individual subject data listings. These results will not be summarized. Clinically significant abnormal laboratory findings will be reported as AEs.

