12 LIST OF APPENDICES

Appendix A: Analysis Visit Windows for Safety and Efficacy Assessments

Table 12-1 Analysis Visit Windows for Safety and Efficacy Assessments

Assessment	Visit ¹	Target Study Day per the protocol	Analysis Visit Window (in study days)
Safety Assessment			
Hematology	Baseline	1	[Screening visit, Pre-dose Day 1]
Serum Chemistry	Week 3	22	[1*, 32]
	Week 6	43	[33, 57]
	Safety Follow-up Visit	N/A	Nominal
Coagulation	Baseline	N/A	[Screening visit, Pre-dose Day 1]
	Week 6	43	[1*, 57]
	Safety Follow-up Visit	N/A	Nominal
Standard 12-Lead ECG	Baseline	1	[Screening visit, Pre-dose Day 1]
	Day 7	7	[1*, 57]
	Safety Follow-up Visit	N/A	Nominal
Vital Sign	Baseline	1	1
	Day 7	7	[2, 14]
	Week 3	22	[15, 32]
	Week 6	43	[33, 57]
	Safety Follow-up Visit	N/A	Nominal
C-SSRS	Baseline	1	[-1, 1]
	Day 7	7	[2, 14]
	Week 3	22	[15, 32]
	Week 6	43	[33, 57]
	Safety Follow-up Visit	N/A	Nominal

Table 12-1 Analysis Visit Windows for Safety and Efficacy Assessments

Assessment	Visit ¹	Target Study Day per the protocol	Analysis Visit Window (in study days)
Efficacy Assessment			
NRS via daily diary	Baseline	N/A	[-7, -1] ²
DSIS via daily diary	Week 1	N/A	[1*, 7]
	Week 2	N/A	[8, 14]
	Week 3	N/A	[15, 21]
	Week 4	N/A	[22, 28]
	Week 5	N/A	[29, 35]
	Week 6	N/A	[36, 42]
NRS reported at study visits	Baseline	1	Before first dose of study drug
PGIC			
	Day 7	7	[1*, 14]
	Week 3	22	[15, 32]
	Week 6	43	[33, 57]
	Safety Follow-up Visit	N/A	Follow the individual visit window to be mapped to individual visits if measured before / on Day 57 or remain as SFU if otherwise.

1* only include day 1 post-dose measurements.

¹ Visit name for analysis purpose is used to report data in tables and figures.

²Only include 7 day measurements before the randomization day.

Notes:

The analysis visit windows will be applied using the following rules for both scheduled and unscheduled visits:

1. If no numerical measurement is available within a visit window, the measurement will be considered missing for the visit.
2. If there is more than 1 numerical measurement available within the same visit window, use the following rules:
 - a. a. For efficacy assessments: if there are multiple measurements within a visit window,
 - i. The measurement closest to the target day will be used; or
 - ii. If there are multiple measurements within the same distance from the target day, the latest measurement will be used.
 - b. For safety assessments: if there are multiple measurements within a visit window,

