 - i. The measurement closest to the target day will be used; or
 - ii. If there are multiple measurements within the same distance from the target day, the latest measurement will be used.
3. When define efficacy and safety at baseline, refer to the generic baseline definition in Section 9.1. If the first dose time is missing, baseline will be defined as the most recent nonmissing measurement collected before the date of the first dose of study drug. For vital sign, there is no time collected and Day 1 will be baseline. For CSSR-S, baseline will be defined as the most recent nonmissing measurement collected before/on Day 1.
4. If the first dose time is missing, use the first dose date to determine post-dose measurements.

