Appendix D: Threshold Value Criteria

Table 12-3 Threshold Value Criteria for Laboratory Tests

Parameter	Comments	
Clinical Chemistry		
ALT	$\leq 3 \times \text{ULN}$ * (Not a PCS criterion) $>3x$ to $\leq 5x\text{ULN}$ $>5x$ to $\leq 8x\text{ULN}$ $>3x\text{ULN}$ $>5x\text{ULN}$ $>8x\text{ULN}$	FDA DILI Guidance Jul 2009.
AST	$\leq 3 \times \text{ULN}$ * (Not a PCS criterion) $>3x$ to $\leq 5x\text{ULN}$ $>5x$ to $\leq 8x\text{ULN}$ $>3x\text{ULN}$ $>5x\text{ULN}$ $>8x\text{ULN}$	FDA DILI Guidance Jul 2009.
ALT or AST	ALT $>3x\text{ULN}$ or AST $>3x\text{ULN}$	Vertex LFT working group 2014. To be counted within the same treatment period.
Alkaline Phosphatase	$>1.5x\text{ULN}$	FDA DILI Guidance Jul 2009.
Total Bilirubin	$>1.5x$ to $\leq 2x\text{ULN}$ $>2x\text{ULN}$	FDA DILI Guidance Jul 2009.
ALT and Total Bilirubin	ALT $>3x\text{ULN}$ and TBILI $>2x\text{ULN}$	FDA DILI Guidance Jul 2009. To be counted within a same treatment period.
AST and Total Bilirubin	AST $>3x\text{ULN}$ and TBILI $>2x\text{ULN}$	FDA DILI Guidance Jul 2009. To be counted within a same treatment period.
(ALT or AST) and Total Bilirubin	(ALT $>3x\text{ULN}$ or AST $>3x\text{ULN}$) and TBILI $>2x\text{ULN}$	Vertex LFT working group 2014. To be counted within the same treatment period.
CK	$>3x$ to $\leq 10x\text{ULN}$ $>10x\text{ULN}$	FDA criteria Feb 2005. Am J Cardiol April 2006.
Creatinine	$\geq 150 \text{ }\mu\text{mol/L}$ (Adults) $\geq 30\%$ change from baseline $\geq 100\%$ change from baseline	Benichou C., 1994.
Blood Urea Nitrogen	$\geq 17 \text{ mmol/L}$	
Chloride	$<85 \text{ mmol/L}$ $>115 \text{ mmol/L}$	
Sodium	$\leq 129 \text{ mmol/L}$ $\geq 150 \text{ mmol/L}$	

Table 12-3 Threshold Value Criteria for Laboratory Tests

Parameter		Comments
Potassium	<3 mmol/L ≥5.5 mmol/L	FDA Feb 2005.
Glucose		
Hypoglycaemia	<2.2 mmol/L	CTCAE criteria.
Hyperglycaemia	>13.9 mmol/L (fasted)	CTCAE criteria.
Albumin	≤25 g/L	
Thyrotropin	< LLN > ULN	
Cholesterol	≥20% increase from baseline	D. M. Hegsted and Robert J. Nicolos, 1987 Demacker PN et al., 1982.
Triglycerides	≥20% absolute change from baseline	D. M. Hegsted and Robert J. Nicolos, 1987 Demacker PN et al., 1982.
Low-density lipoprotein-direct	≥20% increase from baseline	D. M. Hegsted and Robert J. Nicolos, 1987 Demacker PN et al., 1982.
High-density lipoprotein	≥ 20% decrease from baseline	D. M. Hegsted and Robert J. Nicolos, 1987 Demacker PN et al., 1982.
Hematology		

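### SAP 9.4.2 counts laboratory threshold events by arm only visit by visit, while Appendix D counts its four liver composites within a treatment period, and no any-time count is planned

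*SAP*

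**What the plan says.** **The by-arm table.** SAP 9.4.2 states: "The number and percentage of subjects with at least 1 hematology and clinical chemistry laboratory measurement meeting the threshold value criteria will be summarized". The sentence ends "by treatment group at each scheduled visit. Coagulation results will be summarized" (the second half of that quote opens the next sentence, on coagulation). Protocol 12.3.4.2 uses the same unit: the "event will be summarized by treatment group at each scheduled time point". Neither document specifies an any-time or worst-value laboratory table.

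**Unscheduled values.** SAP 9.1 admits them to the analysis in several ways, two of which matter here: "In scheduled visit windows per specified visit windowing rules" and "In the derivation of maximum/minimum on-treatment values and maximum/minimum change from baseline values for safety analyses". SAP 9.4.3 builds a categorised on-treatment maximum for QT/QTcF. SAP 9.4.2 builds nothing of the kind for laboratory values.

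**One value per window.** For chemistry and hematology, Appendix A sets a Week 3 window (target Day 22, post-dose Day 1 to Day 32) and a Week 6 window (target Day 43, Days 33 to 57). The Safety Follow-up Visit is taken at its nominal label. The notes say "The analysis visit windows will be applied using the following rules for both scheduled and unscheduled visits". For safety data, rule 2b says "The measurement closest to the target day will be used", with ties going to the later value.

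**Liver composites.** In Appendix D, Table 12-3, the ALT-and-bilirubin and AST-and-bilirubin rows carry the comment "To be counted within a same treatment period". The ALT-or-AST row and the row combining either transaminase with bilirubin carry the same instruction in almost the same words. No other laboratory row does.

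**The concern.** There are two separate problems.

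The first is a contradiction. Appendix D fixes the counting unit for the four composites as a treatment period, and the only planned table uses a visit. One table cannot satisfy both. The composites with bilirubin are the rows where the difference can make a case vanish, because the two components may cross their limits at different visits.

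The second is a loss of information that can affect any analyte. Where a window holds several values, the one used is chosen by its distance from the target day and not by its severity. An unscheduled sample taken to follow up an abnormal result may be the highest value a subject has, and it can be passed over for a milder scheduled value.

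Per-visit rows also cannot be added to give the number of subjects who ever met a criterion, since one subject may appear in more than one row. At stake is whether the by-arm laboratory safety table shows how many subjects crossed each limit on each arm.

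**Working it through.** The plan states no figure to reproduce here. The check applies the Appendix A rule to hypothetical subjects and compares the SAP 9.4.2 per-visit count with a count over the treatment period. All laboratory values below are invented for illustration, in multiples of ULN.

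**Rule applied.** In each window keep the value with the smallest |day − target|, and on a tie the later one.

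**1. Composite split across visits**
- Day 22: ALT 4, bilirubin 1.2. Day 43: ALT 2, bilirubin 2.5.
- Week 3 combined row: ALT 4 > 3 but bilirubin 1.2 is not > 2, so not counted.
- Week 6 combined row: bilirubin 2.5 > 2 but ALT 2 is not > 3, so not counted.
- Within the period: ALT > 3 and bilirubin > 2 are both met. Count is 1, against 0 at each visit.
- The single-analyte rows still count the subject: ALT at Week 3, bilirubin at Week 6.

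The same can happen in all three composites that include bilirubin. In the ALT-or-AST row one abnormal kept value is enough, so nothing is lost through splitting. There the mismatch is only that visit rows do not give a period count.

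**2. Peak on an unscheduled sample**
- ALT 2.5 on Day 22, 6 on Day 26: distances 0 and 4, Day 22 kept. Per-visit 0, period 1.
- ALT 6 on an unscheduled Day 8, normal on Days 22 and 43: distances 14 and 0 in the Week 3 window, Day 22 kept. Per-visit 0, period 1.
- ALT 4 on Day 22 with bilirubin not above 2, then ALT 9 and bilirubin 2.5 on Day 25: distances 0 and 3, Day 22 kept. The subject is counted in the band above 3 and up to 5, but not in the row above 8 and not in the combined row.
- ALT 2.5 on Day 19, 6 on Day 23: distances 3 and 1, Day 23 kept. The peak is counted.
- ALT 2.5 on Day 20, 6 on Day 24: distances 2 and 2, later value kept. The peak is counted.

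**3. How often a re-test would be passed over (assumed grid)**
Assume the scheduled visit falls within 3 days of target and the re-test comes 2 to 7 days later, all combinations equally likely. That is 2 targets × 7 visit days × 6 gaps = 84 combinations. The re-test is kept in 5, 3 and 1 of the 6 gaps when the visit is 3, 2 and 1 days early, and in none when the visit is on target or late. Kept: 2 × (5 + 3 + 1) = 18. Passed over: 84 − 18 = 66, and 66/84 = 79%. This is the share of re-tests not used, not of events lost: a re-test that is no worse than the kept value changes no count.

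**4. Weight of one subject**
Maximum size: 114/2 = 57 per arm, 1/57 = 1.8%. Minimum size: 62/2 = 31 per arm, 1/31 = 3.2%.

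**The case against.** The strongest reply to the windowing part is that SAP 9.4.2 counts subjects with one or more qualifying measurements. That wording has nothing to do if each window holds a single value, so it may mean any value in the window. On that reading the Day 8, Day 25 and Day 26 peaks above would all be counted at Week 3. This stands as an ambiguity: rule 2b points the other way and the SAP does not say which governs. It does not rescue the composite split across visits, because the table is still per visit.

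Nor are these values hidden. The SAP 9.4.2 listing covers every subject meeting a criterion at any visit and includes unscheduled data. Clinically significant findings become adverse events, which SAP 9.4.1 tabulates by arm without visit windows. Both points are correct. But a listing is not a by-arm count, and Protocol 13.1.1.2 leaves clinical significance to the investigator. The study is also a proof of concept, and no planned decision rests on this table.

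A reader might infer more than the documents support:
- That every re-test peak is lost. It is kept when it is nearer the target day, or tied and later.
- That unscheduled values reach only the listing. SAP 9.1 and Appendix A put them through the visit windows.
- That Appendix D contradicts 9.4.2 for CK, creatinine or cell counts. The treatment-period comment is on the four liver composites alone. For other analytes an any-time count is an improvement, not the repair of a contradiction, and the protocol itself planned counts by time point.
- That Appendix D means the treatment-emergent period. It says treatment period and does not define it. SAP 7.1 separates the 6-week Treatment Period from the 28-day Safety Follow-up, whereas the treatment-emergent period in SAP 9.1 normally runs through the Safety Follow-up Visit.

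**Conclusion.** The concern holds in two parts of different strength.

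For the four liver composites, SAP 9.4.2 and Appendix D use different counting units and must be reconciled. In the three composites with bilirubin, following 9.4.2 can give 0 where Appendix D gives 1. This takes the Appendix D comment at its word: both components need only fall in the same period, not at the same visit.

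For all laboratory criteria, the by-arm count can miss an unscheduled peak if rule 2b governs, and the SAP leaves that open. How many subjects this would affect cannot be derived, because the documents give no event rates or re-test frequencies. The 79% figure rests wholly on the assumed grid. One missed subject is 1.8% of an arm at the maximum size and 3.2% at the minimum.

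The point affects descriptive safety reporting only. It does not touch the efficacy analysis. It is worth correcting before database lock because the data are already collected and SAP 9.1 and 9.4.3 already use on-treatment maxima.

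**What to change.** In SAP 9.4.2:
- Add, for each Appendix D laboratory criterion, the number and percentage of subjects in each arm who meet it at any time after first dose. Use all scheduled and unscheduled values and count each subject once, at the worst category.
- State that rule 2b of Appendix A does not apply to this summary.
- Evaluate the four liver composites over one explicitly defined period, and reconcile the treatment period named in Appendix D with the treatment-emergent period in SAP 9.1.
- Keep the per-visit rows, and say whether they use the single kept value or any value in the window.

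The cost is a few sentences and one extra summary table. No new data are needed. Protocol 12.3.4.2 is not contradicted, since its per-time-point counts remain.
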